12.3. Serious Adverse Events

Adverse events will be reported within 24 hours to the Study PI, the local IRB and the sponsor.

Additional procedures are warranted for cases of serious adverse events which is defined by the FDA as an adverse event that:

- a) Led to death,
- b) Led to serious deterioration in the health of the subject, that either resulted in:
 - 1) A life-threatening illness or injury, or
 - 2) A permanent impairment of a body structure or a body function, or
 - 3) In-patient or prolonged hospitalization, or
 - 4) Medical or surgical intervention to prevent life-threatening illness or injury or permanent impairment to a body structure or a body function,
- c) Led to fetal distress, fetal death or a congenital abnormality or birth defect

12.4. Reporting Procedures

All device related serious adverse events should be reported to the PI, Sponsor, GWU IRB, and FDA.

Unanticipated adverse events should be reported to the PI, Sponsor, and GWU IRB in a timely manner.

13. HYPOTHESIS AND ANALYSIS

13.1. Study Hypothesis

Aim 1: We hypothesize that initiation of MCC pilot study will be feasible defined by outcomes related to (A) implementation, (B) Practicality and (C) Integration.

Aim 2: We hypothesize that MCC will meet established quality measures ($\geq 90\%$) for visualization of stomach anatomy landmarks.

Aim 3: We hypothesize that the MCC will be similar to EGD at visualization of gastric lesions and/or disease.

13.2. Sample Size Considerations

The sample size for this Proof of Concept study was not chosen for statistical consideration, as there are no formal statistical inferences planned. The size of the study is judged adequate for the preliminary evaluation objectives. All 72 participants will receive the MCC and will be referred to follow-up EGD. The base-line prevalence of lesions and the estimated loss to follow-up will provide information for formal sample size calculation for follow-up study.

We did not use a statistical justification but a practical justification to choose 72 participants. All 72 will get the MCC unless they are unable to tolerate the capsule. The issue of drop-out is relevant only to Aim 3 which pilots the concept of non-inferiority compared to subsequent EGD. We did not power this study to prove non-inferiority --- this study will allow us to estimate baseline lesion prevalence and the likely drop-out rate. Moving forward, we will be able to calculate an accurate sample size for a future larger definitive non-inferiority study.

For patients in whom visualization is limited by incomplete gastric emptying, we will record fasting time but exclude patient from assessment of MCC accuracy.

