4. PROTOCOL SUMMARY

Title:	Magnetically Controlled Capsule For Assessment Of Gastric Mucosa In Symptomatic Patients: “MAGNET”
Précis:	This is a single-center prospective study examining the diagnostic utility of a single-use ingestible magnetically controlled capsule (MCC) endoscope (NaviCam™, AnX Robotica) which is remotely controlled by external hardware and software to visualize the mucosa of the stomach on patients with upper abdominal symptoms. Participants will be enrolled and tested at a central site referred from Emergency Departments (EDs), urgent cares (UCs) and primary care practices (PCPs) in the Washington, DC area and additional site(s) to be named. Total enrollment is estimated to be 72 patients with a goal of following all patients with a traditional endoscopy to confirm findings. Aim 1 is to establish feasibility of this novel outpatient testing. Aim 2 is to demonstrate high-quality visualization of gastric anatomic landmarks. Aim 3 is a pilot study to compare visualization of gastric anatomic landmarks and lesions of MCC follow-up traditional EGD. We currently anticipate enrolling 2-3 patients per week over 30 weeks.
Objectives:	
Aim 1: We aim to demonstrate feasibility of MCC in an outpatient primary and urgent care setting. Measured outcomes include duration of MCC test, linkage with EGD follow-up, image storage, image transfer, technician learning curve and documentation.
 
Aim 2: We aim to show that MCC can identify and photograph regions of stomach consistent with established visualized scoring systems for anatomic landmarks.
 
Aim 3: Pilot assessment of MCC compared to subsequent EGD to detect anatomic regions and gastric mucosal lesions.

Population:	An unselected pool of adult patients with an appropriate indication for upper endoscopy such as epigastric pain/burning, nausea and or vomiting, bloating, heartburn, iron deficiency anemia, unintended weight loss, abnormal imaging suggesting organic disease. In general, participants will be age ≥ 18 , mixed gender, mixed race, hemodynamically stable with possible co-morbidities.
Site Number	1
Study Duration:	Time needed to reach sufficient study subjects plus additional time for analysis
Subject Duration:	30 days
Estimated Time to Complete:	12 months

5. SCHEMATIC OF STUDY DESIGN:

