6.2. Rationale

In the United States, upper endoscopy is frequently performed for a variety of symptoms including heartburn, bloating, nausea, burping, and epigastric pain/burning. The prevalence of these symptoms may provide as much as 25% of a gastroenterologist's office practice. In general, the diagnostic yield of an EGD is low. Without alarm symptoms, as many as 70% of procedures are negative for significant findings. One major indication is testing for *H. pylori* for which EGD may be unnecessary, because *H. pylori* detection can be accomplished by fecal antigen testing or breath testing as accurately as biopsy and less expensively.

We believe there is an opportunity to improve the risk stratification of patients that undergo endoscopy through the use of MCC. Our primary hypothesis is that MCC allows for visualization of the stomach of symptomatic patients referred from the emergency, urgent care and primary care settings with clinical symptoms appropriate for endoscopy. A prospective study is proposed to evaluate the feasibility, safety and accuracy of this novel diagnostic modality.

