6.3. Potential Risks and Benefits

6.3.1. Potential Risks

Patients for whom study enrollment may interfere with standard clinical care will not be enrolled. Alternatives to study participation are for patient to receive standard of care treatment for symptoms which includes only an EGD or barium studies. We have considered a variety of potential risks to participants including cognitive, affective,

physical, legal/confidentiality and economic risks. The NaviCam MCC is manufactured by AnX Robotica and has been granted marketing authorization by the FDA through the de-novo process to confirm its safety and effectiveness profile.

Since its introduction to the Chinese market after being approved by the Chinese Food and Drug Agency (CFD) in 2012, the NaviCam MCC was subject to a series of clinical studies. Published studies involving more than 500 people in China have been published comparing MCC to gastroscope. In a pilot study in 34 healthy volunteers (Liao et al. 2012), 75 to 100% of gastric mucosa was visualized in 27 (79.4%) people and 50% to 75% in 7 (20.6%) people. Visualization of the gastric cardia, fundus, body, angulus, antrum and pylorus were subjectively assessed as complete in 82.4%, 85.3%, 100.0%, 100.0%, 100.0% and 100.0% respectively. In a non-blinded comparative study in 68 patients (Zou et al. 2015) showed a diagnostic accuracy similar to standard gastroscopy: the positive percent agreement was 96.0%, and the negative percent agreement was 77.8%. The overall agreement was 91.2% with a κ value of 0.765 ($p<0.001$). A total of 68 pathological findings were detected, of which 53 were identified by both methods. In a multi-center comparative study in 350 patients (Liao et al. 2016), the NaviCam detected gastric focal lesions in the whole stomach with 90.4% sensitivity, 94.7% specificity, a PPV of 87.9%, a NPV of 95.9% and 93.4% accuracy. The NaviCam was preferred by almost all patients (95.7%), compared with gastroscopy. (Liao, 2016).

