8. STUDY OUTCOME MEASURES

8.1. Primary Outcome:

Aim 1: Pilot and Feasibility Stage.

- 1) *Implementation:* Installation, Training, Site Requirements
- 2) *Practicality:* Duration of MCC test (minutes), Technician “learning curve,” Clinical Staff and Patient Satisfaction, Duration of fasting required
- 3) *Integration:* Scheduling MCC, Linkage with EGD follow-up, Image storage, Image transfer, Documentation of Interpretation, Photo-documentation, Database development

Aim 2: High-Quality Visualization (90%) of Gastric Anatomic Landmarks

Defined as visualization and photo-documentation of the following anatomical landmarks:

- 1) Lower Esophagus / Z line
- 2) Cardia / fundus
- 3) Body, lesser curvature AND/OR Body, greater curvature
- 4) Anterior / Posterior walls
- 5) Angularis
- 6) Antrum
- 7) Pylorus
- 8) Duodenal Bulb
- 9) Duodenal Ampulla

Aim 3: MCC versus EGD for visualization of anatomic landmarks (see above) and gastric lesions in symptomatic patients

Defined as visualization and photo-documentation of the following structures and diseases:

- 1) Visible Lesions (Paris Classification if relevant)
- 2) Ulcers (Forrest Classification) erosions
- 3) Gastric Atrophy
- 4) Gastric Varices
- 5) Gastritis*
- 7) Submucosal lesions
- 8) “Does patient need a follow-up EGD?” Y/N (Opinion of endoscopist interpreting MCC based on MCC findings.)

* (not erythema but ‘chicken wire’ pattern intramucosal change in vascular pattern or hemorrhagic)

8.2. Secondary Outcomes:

- (1) Cost-effective analysis

- (2) 30-day follow-up for adverse events and safety
- (3) Patient Satisfaction of MCC versus EGD
- (4) Replication of similar sensitivity and specificity of MCC to EGD to prior trials outside of the US for (a) Ulcers; (b) Cancer; (c) Inflammatory Changes
- (5) Time spent visualizing the stomach for MCC versus EGD (minutes)
- (6) Visualization of the duodenum
- (7) Hiatus hernia

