9.3. Patient Safety

The study will be conducted in compliance with the Declaration of Helsinki, ICH-GCP guidelines, ISO 14155, and US regulations. Study design will be approved by the local IRB at each participating institution prior to commencement.

9.4. Study procedure:

1. Screen potential adult patients with an appropriate indication for upper endoscopy such as epigastric pain/burning, nausea and or vomiting, bloating, heartburn, iron deficiency anemia, unintended weight loss, abnormal imaging suggesting organic disease from a larger pool of patients seen in an ED, Urgent Care, Primary Care and GI Clinic patients. In some settings, a research assistant will be on site to perform the screen. In other settings, the clinical staff will perform the screen or potential patients will be contacted by phone by RC. (Form used: *Magnet 1*)
2. Patients screened who are eligible will be approached about potential interest. (See *full list of inclusion/ exclusion criteria*). In some circumstances, patients will be given contact information for the research coordinator (RC), who will contact them as soon as possible to schedule MCC. In other circumstances, the research assistant will contact RC and attempt to schedule MCC before patient leaves the clinical setting.
3. RC will contact patients to complete screening, confirm eligibility, obtain verbal consent, and schedule both MCC and EGD (if EGD is not already scheduled). Formal written consent will be obtained by patient at the MCC location ([name]).
4. Participants arrive at the MCC location for final screen, sign written consent and undergo MCC. All consented patients will be given a study ID and recorded in enrollment log. (Form used: *Magnet 3*) The patient's demographics and images will be stored in a HIPAA compliant fashion.
 - BRIEF DESCRIPTION OF MCC PROCEDURE. The patient will be NPO midnight. They will come to the facility and will ingest the capsule per manufacturer's protocol. (Manufacturer's protocol says that the person will take 10ml of simethicone in 100ml of water 40min before capsule is ingested. The capsule will then be controlled externally by magnetic field by the examining health care provider in such a way that the major regions of the stomach are photo-documented with still images and video. This may involve changing the position of the patient and the

possible ingestion of additional water. The sequence of the examination

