will be pre-determined, and each area will have a predetermined number of images obtained as suggested by Gastroenterology Society guidelines.

5. Patient data collected will include the following elements: chief complaint of patient, history of present illness, past medical history, current medications (only PPIs and pain medication)..
6. At completion of MCC, video will be archived and patient satisfaction will be assessed. Capsule endoscopy will NOT be used for clinical decisions.
7. Patients will be instructed to return to the physician sooner, if concerning signs develop. A 7 and 30-day follow-up call and chart review is only performed if person is lost to follow-up will be conducted to check for symptom resolution and adverse events.
8. Esophagogastroduodenoscopy (EGD) will be performed as soon as possible in an appropriate endoscopy facility by an experienced endoscopist.
9. Endoscopic images will be stored in secure serve for later comparison with MCC images.

Summary of Research Strategy

- ❖ PRE-SCREEN (DAY -7 to DAY -1)
 - Upper Abdominal Pain or Related Symptoms (Indications for an EGD)
 - Performed in ED, UC, PCP offices or GI clinic
- ❖ SCREEN (DAY -7 -> DAY 0)
 - More thorough screening questions and scheduling by RC (<24 hours)
 - Performed by Telephone
- ❖ ENROLL (DAY 0)
 - Signed Informed Consent procedure, more detailed questions and MCC Procedure performed
 - Occurs at the GWU Medical Faculty Associates Building on [name].
 - NaviCam MCC performed by trained Clinician.
 - Reviewed by a Gastroenterologist.
 - Scheduled for an EGD will ideally be performed within 5 days of the MCC procedure, but will allow MCC procedure to be performed up to 14 days either before or after an EGD (paid by insurance as standard of care).
- ❖ FOLLOW-UP (DAY 1-30)

- Day 7 and Day 30: Telephone Call plus CRISP Chart Review, only if lost to follow-up.

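### Section 13.2 removes participants whose MCC view is limited by incomplete gastric emptying, so the MCC-versus-EGD accuracy figures leave out failures of the MCC examination itself

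*Protocol*

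**What the plan says.** The rule is the last paragraph of protocol section 13.2: "For patients in whom visualization is limited by incomplete gastric emptying, we will record fasting time but exclude patient from assessment of MCC accuracy". The same section says "All 72 participants will receive the MCC and will be referred to follow-up EGD", describes the trial as a proof of concept without formal inference, and says Aim 3 pilots the idea of non-inferiority to EGD.

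Other parts of the protocol bear on the rule:

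- **Preparation.** Section 8.3.3 sets the overnight fast under the heading of MCC preparation, and section 9.4 includes it in the description of the MCC procedure: "The patient will be NPO midnight. They will come to the facility and will ingest the capsule".
- **Outcomes affected.** Aim 3 (section 8.1) compares MCC with EGD for gastric lesions. Secondary outcome 4 (section 8.2) is "Replication of similar sensitivity and specificity of MCC to EGD to prior trials outside of the US".
- **Population.** Section 4 describes it as "An unselected pool of adult patients with an appropriate indication for upper endoscopy".
- **Order of the tests.** Section 13.2 speaks of a subsequent EGD, but the research strategy summary in section 9.4 "will allow MCC procedure to be performed up to 14 days either before or after an EGD".
- **Entry criteria.** Section 10.2 already excludes gastroparesis.

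**The concern.** The exclusion depends on how the index test turned out. A participant who fasted as instructed, swallowed the capsule and gave a poor view because of residue has had an MCC examination that worked badly. A clinic using MCC would meet the same case. Leaving it out answers a narrower question than whether MCC and EGD are comparable in symptomatic patients with an indication for EGD, which section 6.1 gives as the goal.

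The rule acts on one side only: a limited MCC view removes the participant, and nothing equivalent is stated for EGD. If lesions are harder to see in a poorly emptied stomach, the remaining participants show MCC at its better end. Comparison with EGD, and with the earlier trials abroad, then tilts in favour of MCC.

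The decision is also open to influence. Section 13.2 does not say what counts as limited. Because MCC may follow EGD by up to 14 days, the EGD result may already be known when a view is judged.

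**Working it through.** **The plan's own figures.** There is no derivation to reproduce. Section 13.2 gives a practical reason for 72 participants and states neither an expected share with limited views nor a target sensitivity. The effect can only be illustrated.

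**Inputs from the protocol**

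- Sensitivity and specificity in those retained: section 6.3.1 reports that in a multicentre study "the NaviCam detected gastric focal lesions in the whole stomach with 90.4% sensitivity, 94.7% specificity".
- Rough lesion prevalence: section 6.2 says "Without alarm symptoms, as many as 70% of procedures are negative for significant findings", which leaves about 30% positive.
- Number examined: 72 (section 13.2).

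**Assumptions, not in the protocol**

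- *f*: share of EGD-positive participants (or of EGD-negative participants, for specificity) removed by the rule.
- *d*: proportion of lesions MCC detects among the excluded EGD-positive participants.
- EGD follow-up is complete.

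**Sensitivity over everyone examined** = 0.904 × (1 − *f*) + *d* × *f*. For *f* = 10% and *d* = 0 this is 0.904 × 0.90 = 0.8136.

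| *f* | *d* = 0 | *d* = 50% | *d* = 90.4% | *d* = 100% |
|---|---|---|---|---|
| 5% | 85.9% | 88.4% | 90.4% | 90.9% |
| 10% | 81.4% | 86.4% | 90.4% | 91.4% |
| 15% | 76.8% | 84.3% | 90.4% | 91.8% |

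Under the rule the reported figure is 90.4% in every cell. The overstatement is *f* × (0.904 − *d*). At *f* = 10% it is 9.0 points when *d* = 0 and zero when *d* = 90.4%; it reverses slightly, by 1.0 point, when *d* = 100%.

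**In counts.** 0.30 × 72 = 21.6, so about 22 participants have a lesion, and 10% of 22 is about 2 excluded.

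- Reported under the rule: 18/20 = 90.0%, exact (Clopper-Pearson) 95% interval 68.3% to 98.8%.
- Over all 22: 18/22 = 81.8%, 19/22 = 86.4% or 20/22 = 90.9%, if 0, 1 or 2 of the excluded lesions were seen.

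If prevalence were 50% instead, 36 would have a lesion and about 4 would be excluded. The reported figure would be 29/32 = 90.6% (interval 75.0% to 98.0%), against 29/36 = 80.6% to 33/36 = 91.7%. Prevalence changes the precision but hardly changes the shift.

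**Specificity** from 94.7% at *f* = 10%, with no lesion seen in the excluded EGD-negative participants:

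- Coded as negative: 0.947 × 0.90 + 0.10 = 0.9523, or 95.2%.
- Not counted as true negatives: 0.947 × 0.90 = 0.8523, or 85.2%.

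The direction for specificity therefore depends on the coding, which is why both versions need to be shown.

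**The case against.** The strongest reply is that this is a pilot without formal inference. Section 13.2 names lesion prevalence and drop-out, not MCC sensitivity, as what it will supply for the later study, and the illustrated shift lies well inside the sampling error. Accuracy given adequate preparation is a recognisable quantity. Preparation failure is not wholly hidden either, since fasting time is recorded and the duration of fasting required is an Aim 1 outcome. Gastroparesis is excluded at entry, so few participants may be affected.

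This limits how serious the point is, but it does not remove it. A descriptive estimate can still be biased, and section 20 lists a non-inferiority publication on gastric lesions. Recording fasting time does not return anyone to the accuracy figures.

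Further points have partial force:

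- The definition of a limited view could stand in an analysis plan or in the assessment forms, which are not shown. Its absence from section 13.2 is therefore secondary. The exclusion itself is stated outright.
- The protocol does not say that whoever judges the view sees EGD results. Such knowledge is possible under the 14-day window, not established.
- The 30% prevalence is rough. The source sentence concerns patients without alarm symptoms, whereas section 10.1 admits anemia and weight loss, and section 8.1 counts gastritis and atrophy. The cited 90.4% concerns focal lesions only.
- The rule is triggered by an impaired view, not by residue as such, so participants with residue but a clear view stay in.

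It may also be objected that a non-diagnostic examination is not a negative reading, so counting it as a miss is harsh. For sensitivity the label makes no difference: a lesion not seen was not detected. Only specificity depends on the coding.

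**Conclusion.** The concern holds. Section 13.2 states the exclusion and nothing elsewhere in the protocol reverses it. It takes failures of the MCC examination out of the Aim 3 lesion comparison and secondary outcome 4, which are the natural reading of MCC accuracy, a term the section does not define. It will tend to overstate sensitivity whenever lesions are harder to see in a poorly emptied stomach.

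The protocol does not allow the size to be fixed. With 5% to 15% of lesion-bearing participants excluded, and between none and half of their lesions seen, the overstatement runs from 2.0 to 13.6 points. It is nil if detection is unaffected. This assumes that 90.4% holds in those retained. At this sample size the shift is smaller than the sampling error, but it would persist in a larger study that kept the same rule. It should be fixed, but it does not undermine the trial.

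**What to change.** Replace the exclusion sentence in section 13.2 with the following:

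1. Every participant with both MCC and EGD stays in the main accuracy analysis.
2. EGD-positive: a lesion seen on MCC counts as detected and one not seen counts as not detected, whatever the emptying.
3. EGD-negative: a lesion seen on MCC is handled as in any other participant. A limited examination with no lesion seen is reported in its own row, and specificity is given both with it coded as negative and with it not counted as a true negative.
4. The criterion for a view limited by incomplete emptying is written down beforehand and applied from the MCC recording by a reader who does not know the EGD result. The two independent readers foreseen in section 8.3.6 could do this.
5. The number so classified is reported by EGD result.
6. The estimate restricted to adequate emptying is kept as a labelled sensitivity analysis.

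The cost is one paragraph, one extra table and a masked classification from stored video. No new visits are needed. The main accuracy figures may come out slightly less favourable.

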13.3. Cost-Effective Analysis

A cost-effective model will be constructed to compare MCC with traditional endoscopy. Full analysis plan is forthcoming.

14. STUDY OVERSIGHT

A Data Safety Monitoring Board (DSMB) consisting of appropriately qualified independent experts has been appointed by the PI to provide review of data on patient safety and study progress. The membership roster is maintained by site PI and study coordinator and is available from them as needed. PI will provide reports including adverse events.

The Data and Safety Monitoring Board provides ongoing evaluation of the study progress including patient accrual and retention, monitoring of adverse events, and the adequacy and efficiency of the analysis plan to discern outcomes that might require study modifications, or result in early cessation of the study due to its benefits or harms. The DSMB does not evaluate the scientific merit or methodology of the study, nor does it directly participate in the execution of a study's protocol, monitor the budget, or approve sub-protocols or other modifications to the study.

The major responsibilities of the Board are:

- To review the data analysis plan and make recommendations for additions or changes to the plan.
- To assess the performance of the site and make appropriate recommendations regarding continuation, probationary status, or termination.
- To consider patient accrual, overall study progress (timeline and follow-up participation), adverse effects and patient safety, and proper monitoring and reporting by the study team as these affect the ethical treatment of participants or the ethical conduct of research.
- Report to the PI on any perceived problems with study conduct, enrollment, sample size, and data collection.

